8.10.2.2. Process for the suspension of vaccination and/or study modification

In the event that a safety signal is observed, GSK Biologicals' VSMB might decide to suspend further vaccinations in all groups or in selected groups.

In case the vaccination is suspended:

- Subjects who signed an informed consent but have not received any study vaccine will be informed that their study participation will be stopped.
- For all other subjects, all visits will continue as planned for evaluation of the safety and immunogenicity of the vaccine except that Visit 5 on Day 67 will be cancelled if no vaccine dose is administered at Visit 4 on Day 60.

8.10.3. Study holding rules

The safety holding rules which will be checked by the iSRC during each safety evaluation are defined below ([Table 22](#)). Please refer to [APPENDIX C](#) for the definition of the Food and Drug Administration (FDA) Toxicology Grading Scale for laboratory abnormalities in healthy subjects.

These holding rules have been written under the assumption that the safety data will be available from all subjects. If the data from all subjects are not available (i.e. in case a subject is lost to follow-up), then the holding rules will be assessed on a pro-rata basis.

Table 22 List of holding rules

| Holding rule N° | Event | Number of subjects | |
|-----------------|--|----------------------------------|----------------------------------|
| | | Step 1 | Step 2 |
| 1a | Death or any life-threatening SAE | ≥ 1 | ≥ 1 |
| 1b | Any withdrawal from the study (by investigator or subject request) following a Grade 3 AE that cannot reasonably be attributed to a cause other than vaccination | ≥ 1 | ≥ 1 |
| 1c | Any local or general solicited AE leading to hospitalisation , or fever >40°C (104°F) that cannot reasonably be attributed to a cause other than vaccination, or necrosis at the injection site, within the 7-day (Day 0-Day 6) post-vaccination period | ≥ 1 | ≥ 1 |
| 2a | Any Grade 3 solicited local AE lasting 48h or more in an investigational group, within the 7-day (Day 0-Day 6) post-vaccination period | ≥ 5/15 and ≥ 2 subjects/group | ≥ 8/30 and ≥ 2 subjects/group |
| 2b | Any Grade 3 solicited general AE lasting 48h or more in an investigational group, that cannot reasonably be attributed to a cause other than vaccination, within the 7-day (Day 0-Day 6) post-vaccination period | ≥ 5/15 and ≥ 2 subjects/group | ≥ 8/30 and ≥ 2 subjects/group |
| 2c | Any Grade 3 unsolicited AE in an investigational group, that cannot reasonably be attributed to a cause other than vaccination, within the 7-day (Day 0-Day 6) post-vaccination period or Any Grade 3 abnormality in pre-specified haematological or biochemical laboratory parameters* in an investigational group within the 7-day (Day 0-Day 6) post-vaccination period | ≥ 5/15 and ≥ 2 subjects/group | ≥ 8/30 and ≥ 2 subjects/group |

* i.e. haemoglobin, WBC, platelets, creatinine, ALT and AST

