(b) Treatment number allocation with randomisation at Visit 1 (Day 0); treatment number allocation without randomisation at Visit 4 (Day 60).

(c) Only for subjects belonging to the CMI sub-cohort.

(d) Distribution of 2 Diary Cards after each vaccination:

- a 1st one distributed on the day of vaccination for recording of solicited and unsolicited AEs and concomitant medications/ products and vaccinations from Day 0 to Day 6 after each vaccination.
- a 2nd one distributed on the 7 day post-vaccination visit for recording of unsolicited AEs and concomitant medications/ products and vaccinations from Day 7 to Day 29 after each vaccination.

(e) Screening evaluations may be completed 1 to 28 days before Day 0. Site staff should allow sufficient time between the Screening and Visit 1 to receive and review screening safety laboratory test results. If a delay occurs such that the interval between Screening and the Visit 1 vaccination exceeds 28 days, a re-screening visit should be scheduled before Visit 1 during which blood sample collection for safety laboratory assessment must be repeated; an interim medical history and physical examination must be obtained and inclusion / exclusion criteria must be re-reviewed.

(f) Complete physical examination including vital signs.

(g) From Screening to Visit 1, only those SAEs that are considered related to study participation or to concomitant use of GSK products or any fatal events need to be recorded. GSK products or any fatal event need to be recorded.

(h) Concomitant medication products/vaccination as indicated in Section 6.6.1 need to be recorded.

(i) *This test should be repeated on another day if the first attempt doesn't meet quality requirements as described by ATS/ERS standards (Miller, 2005).*

Table 7 Intervals between study visits

| Interval | Optimal length of interval ^(a) | Allowed interval |
|---|---|----------------------------|
| Screening (Pre-Day 0) → Visit 1 (Day 0) | 5 days | 1 – 28 days ^(b) |
| Visit 1 (Day 0) → Visit 2 (Day 7) | 7 days | 7 - 9 days |
| Visit 1 (Day 0) → Visit 3 (Day 30) | 30 days | 30 - 40 days |
| Visit 1 (Day 0) → Visit 4 (Day 60) | 60 days | 60 - 70 days |
| Visit 4 (Day 60) → Visit 5 (Day 67) | 7 days | 7 - 9 days |
| Visit 4 (Day 60) → Visit 6 (Day 90) | 30 days | 30 - 40 days |
| Visit 1 (Day 0) → Visit 7 (Day 210) | 210 days | 210 - 230 days |
| Visit 1 (Day 0) → Visit 8 (Day 420) | 420 days | 420 - 440 days |

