5.7.4.2. Haematology and biochemistry

Table 13 Haematology/ biochemistry

| Blood sampling time point | | Sub-cohort Name | No. subjects | Component |
|--------------------------------|---------------------|-----------------|--------------|--|
| Type of contact and time point | Sampling time point | | | |
| Screening* (Pre-Day 0) | Screening | All subjects | ~120 | Haematology (leukocytes [white blood cells], white blood cell differential count [neutrophils, lymphocytes, eosinophils, basophils, monocytes], erythrocytes [red blood cells], haemoglobin, platelets) |
| Visit 1 (Day 0) | Pre-Vacc I | All subjects | ~120 | |
| Visit 2 (Day 7) | Post-Vacc I | All subjects | ~120 | |
| Visit 4 (Day 60) | Post-Vacc I | All subjects | ~120 | |
| Visit 5 (Day 67) | Post-Vacc II | All subjects | ~120 | |
| Visit 7 (Day 210) | Post-Vacc II | All subjects | ~120 | Biochemistry (ALT, AST, creatinine) |
| Visit 8 (Day 420) | Post-Vacc II | All subjects | ~120 | |

ALT: Alanine aminotransferase; AST: Aspartate aminotransferase

Screening evaluations may be completed 1 to 28 days before Day 0. Site staff should allow sufficient time between the Screening and Day 0 visits to receive and review screening safety laboratory test results. If a delay occurs such that the interval between Screening and the Day 0 vaccination exceeds 28 days, a re-screening visit should be scheduled before Visit 1 during which blood sample collection for safety laboratory assessment should be repeated.

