8.10. Holding rules and safety monitoring

The investigator is not permitted to start the administration of the next dose (Dose2) or next step (Step 2) until receipt of the favourable outcome of the safety evaluation, based on the safety data collected up to seven days after administration of the previous dose(s) (Figure 2).

In order to move to the next step, safety data will be needed from all subjects. In order to move from Dose 1 to Dose 2 within a step, safety data from about 50% of the vaccinated subjects will be needed (Figure 2).

Moreover, if the investigator becomes aware of a holding rule being met, he/she will suspend vaccination and will inform GSK Biologicals Central Safety immediately (within 24 hours) (e.g. in case of SAEs).

Figure 2 Overview of iSRC evaluations

D = day

SE up to Day 7 = safety evaluation based on data up to the Day 7 post-vaccination visit (i.e. Visit 2 at Day 7 and Visit 5 at Day 67), including Day 7 post-vaccination laboratory assessments.

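### The laboratory part of holding rule 2c counts Days 0 to 6 only, but the first scheduled safety sample after each dose is taken on Days 7 to 9, so scheduled samples cannot trigger it as written

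*Protocol*

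**What the plan says.** Rule 2c in Table 22 (Protocol 8.10.3) has two parts, one for unsolicited Grade 3 adverse events and one for laboratory results. The laboratory part reads "Any Grade 3 abnormality in pre-specified haematological or biochemical laboratory parameters* in an investigational group within the 7-day (Day 0-Day 6) post-vaccination period". It covers haemoglobin, WBC, platelets, creatinine, ALT and AST. The threshold is 5 of 15 subjects in Step 1 and 8 of 30 in Step 2, with a floor of two subjects per group.

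Safety blood is scheduled at Screening and on Days 0, 7, 60, 67, 210 and 420 (Protocol 3.1 and Table 13). Table 7 in Section 5.5 sets the intervals for the two visits that follow a dose: "Visit 1 (Day 0) → Visit 2 (Day 7) | 7 days | 7 - 9 days" and "Visit 4 (Day 60) → Visit 5 (Day 67) | 7 days | 7 - 9 days". Table 13 labels the two vaccination-day samples "Visit 1 (Day 0) | Pre-Vacc I | All subjects" and "Visit 4 (Day 60) | Post-Vacc I | All subjects".

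The Figure 2 footnote in Section 8.10 bases each safety evaluation on data up to the Day 7 visit, "including Day 7 post-vaccination laboratory assessments". For moving from Dose 1 to Dose 2 within a step, "safety data from about 50% of the vaccinated subjects will be needed"; moving to Step 2 needs data from all subjects. Where data are incomplete, "then the holding rules will be assessed on a pro-rata basis". The SAP gives no holding-rule window that would change any of this.

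**The concern.** The window in the rule and the timing of the blood draws do not meet. Nor is Day 0 to Day 6 a loose way of saying the Day 7 visit, because the protocol applies that boundary consistently. The first diary card covers the vaccination day and the six days after it, and the second card starts on Day 7 (Section 5.6.16). Table 19 closes the 7-day period at Day 6 and Day 66. A careful reader of rule 2c would therefore leave a Day 7 result out, while a reader of the Figure 2 footnote would expect it to be considered.

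UspA2 has not been given to humans before, and Section 8.10.2 gives first human administration as the reason for appointing the iSRC and defining holding rules. If the laboratory rule cannot be met on the planned samples, a Day 7 cluster of Grade 3 results at or above the stated threshold is handled by judgement, and two people could disagree about whether the rule was met.

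**Working it through.** **1. The plan's own figures.** Section 8.10.4 states numerical operating characteristics for rule 1 only. The probability that it is not met is (1 − p)^n.

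- n = 15, p = 1%: 0.99^15 = 0.8601 (stated: more than 86% below this rate)
- n = 15, p = 20%: 0.80^15 = 0.0352 (stated: less than 3.5% above this rate)
- n = 30, p = 1%: 0.99^30 = 0.7397 (stated: more than 74% below this rate)
- n = 30, p = 10%: 0.90^30 = 0.0424 (stated: less than 4.2% above this rate)

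All four reproduce to rounding, so the exact binomial is the plan's own model.

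**2. Window check, in days after the most recent dose.**

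- Days counted by rule 2c: {0, 1, 2, 3, 4, 5, 6}
- Days allowed for Visit 2 or Visit 5: {7, 8, 9}
- Days in common: none

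The other scheduled samples do not fill the gap:

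- Day 0 is labelled as before the first vaccination.
- Day 60 is labelled as after the first vaccination, and the label for after the second starts only at Day 67. It is therefore the sample before Dose 2, and it is 60 to 70 days after Dose 1.
- Days 210 and 420 are months after either dose.

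The probability that scheduled samples meet the laboratory part is therefore 0 at any true rate. An unscheduled repeat, which Section 5.6.14.1 permits when medically indicated, could still fall on Days 0 to 6.

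**3. What the rule would do if the Day 7 visit counted.** P(met) = P(X ≥ k), with X binomial(n, p). The documents give no Grade 3 laboratory rate, so p is an assumed range. For the Dose 2 gates I assume about half of each group is available and the threshold is scaled pro rata and rounded up:

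- Step 1, n = 8: 5/15 × 8 = 2.67, so k = 3
- Step 1, n = 7: 5/15 × 7 = 2.33, so k = 3
- Step 2, n = 15: 8/30 × 15 = 4, so k = 4

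Every k used exceeds the floor of two subjects per group.

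| Probability that the rule is met (%), by assumed true rate | 5% | 10% | 20% | 30% | 40% | 50% |
|---|---|---|---|---|---|---|
| Complete Step 1 group, at least 5/15 | 0.06 | 1.27 | 16.42 | 48.45 | 78.27 | 94.08 |
| Complete Step 2 group, at least 8/30 | 0.01 | 0.78 | 23.92 | 71.86 | 95.65 | 99.74 |
| Step 1 Dose 2 gate, at least 3/8 | 0.58 | 3.81 | 20.31 | 44.82 | 68.46 | 85.55 |
| Step 1 Dose 2 gate, at least 3/7 | 0.38 | 2.57 | 14.80 | 35.29 | 58.01 | 77.34 |
| Step 2 Dose 2 gate, at least 4/15 | 0.55 | 5.56 | 35.18 | 70.31 | 90.95 | 98.24 |
| As written, scheduled samples, any n | 0 | 0 | 0 | 0 | 0 | 0 |

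At true rates of 10% or less the corrected rule fires at most 5.56% of the time, so little is lost there. The difference becomes material at about 20% and above.

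**The case against.** The best reply is that the section read as a whole supplies the intended meaning. The iSRC checks the holding rules at each evaluation, each evaluation includes the Day 7 laboratory results, and those are the only scheduled post-dose results the rule could be about. A sensible committee would count them. The default is also to hold: neither Dose 2 nor Step 2 may start without a favourable written outcome, so a rule that stays silent does not authorise vaccination. And because rule 2c is counted per group while the clinical evaluators are blinded, it runs through the unblinded iSRC in practice. That committee already has these results and can escalate any signal to the Vaccine Safety Monitoring Board (VSMB) without a Table 22 rule being met.

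The figures can also be questioned. The 8/30 row is not tied to a vaccination gate in the readable text, because no study dose remains after Dose 2 of Step 2. The 50% requirement refers to vaccinated subjects, not to each group. The pro-rata sentence gives loss to follow-up as its case and does not mention a planned partial review.

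These points limit the consequence, and I accept them as limits. They do not make the rule work as printed. That a committee would probably read past the wording confirms that the wording is wrong, and a pre-specified threshold is meant to settle the matter before anyone has seen the data. The 0% result does not depend on the assumed rates or on the per-group counts.

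**Conclusion.** The point holds. For both doses, the laboratory part of rule 2c cannot be met from scheduled samples as written, and it conflicts with the Figure 2 footnote. The gap is confined to the numerical trigger: review of the Day 7 results, escalation on judgement and the requirement for written authorisation all remain. The 0% rests only on the protocol's own windows and on visits being kept within them. The size of the loss rests on assumed Grade 3 rates and, at the Dose 2 gates, on assumed group counts and rounded pro-rata thresholds. It should be corrected, because the rule is a safety decision rule for a first-in-human antigen and at present does nothing on the planned data.

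**What to change.** In Table 22, rule 2c, change the window for the laboratory part only, to: *up to and including the Day 7 post-vaccination visit (Visit 2 or Visit 5, 7 to 9 days after the dose)*. Leave the Day 0 to Day 6 window for the unsolicited adverse event part as it is. This brings the table into line with the Figure 2 footnote. The cost is the wording of one table row. No sample, visit or committee meeting is added, because the Day 7 blood is already drawn and already part of each iSRC evaluation.

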8.10.2. Internal Safety Review Committee

As the investigational vaccine formulation will be administered for first time to human, an iSRC will be appointed in addition to the existing project's SRT and safety holding rules have been defined.

The iSRC, authorised by the GSK Biologicals' Vaccine Safety Monitoring Board (VSMB) will include as core members a GSK Biologicals' Safety Leader, a CRDL and a Biostatistician, who are not otherwise involved in the conduct of the project, in order to maintain the observer-blind to the treatment codes amongst project-related personnel until the final analysis of data.

The iSRC will conduct *unblinded* reviews of all available safety data from the present study, while taking into account any other findings that could have an impact on the safety of the subjects, and will determine whether there is a safety signal that needs to be escalated to GSK Biologicals' VSMB. In the event that a safety signal is observed, GSK Biologicals' VSMB might decide to suspend, modify or continue the conduct of the study in all groups or in selected groups.

To facilitate the safety evaluation, the investigator or his/her designee will need to transcribe the information of the Diary Cards returned at the 7 day post-vaccination visits into the eCRF promptly (preferably within two working days of data availability).

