8.10.2.1. Outcome of safety evaluation

If **no safety signal** is observed, the favourable outcome of the safety evaluation will be documented and provided in writing (scanned and emailed) authorising the investigator to proceed to the next dose and/or step of the trial.

If a **safety signal** is observed during the safety evaluation or if any of the holding rules 1a, 1b, 1c is reported by the investigator at any time, the SRT and iSRC leader is responsible for the urgent communication and escalation of the concern to the GSK Biologicals VSMB who will decide during an *ad hoc* meeting whether to suspend, modify or continue the conduct of the study on all groups or on selected groups. The decision of the GSK Biologicals VSMB will be documented and provided in writing (scanned and emailed) to the investigator regarding the further conduct of the study.

In the event that a safety signal has prompted a GSK Biologicals' VSMB review, further vaccination may resume following, and dependent upon, a decision provided in writing to the investigator (scanned and emailed) authorising the resumption of vaccinations.

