| Random – mg/dL | 110 – 125 | 126 – 200 | >200 | |
| Blood Urea Nitrogen BUN mg/dL | 23 – 26 | 27 – 31 | > 31 | Requires dialysis |
| Creatinine – mg/dL | 1.5 – 1.7 | 1.8 – 2.0 | 2.1 – 2.5 | > 2.5 or requires dialysis |
| Calcium – hypocalcemia mg/dL | 8.0 – 8.4 | 7.5 – 7.9 | 7.0 – 7.4 | < 7.0 |
| Calcium – hypercalcemia mg/dL | 10.5 – 11.0 | 11.1 – 11.5 | 11.6 – 12.0 | > 12.0 |
| Magnesium – hypomagnesemia mg/dL | 1.3 – 1.5 | 1.1 – 1.2 | 0.9 – 1.0 | < 0.9 |
| Phosphorous – hypophosphatemia mg/dL | 2.3 – 2.5 | 2.0 – 2.2 | 1.6 – 1.9 | < 1.6 |
| CPK – mg/dL | 1.25 – 1.5 x ULN | 1.6 – 3.0 x ULN | 3.1 – 10 x ULN | > 10 x ULN |
| Albumin – Hypoalbuminemia g/dL | 2.8 – 3.1 | 2.5 – 2.7 | < 2.5 | -- |
| Total Protein – Hypoproteinemia g/dL | 5.5 – 6.0 | 5.0 – 5.4 | < 5.0 | -- |
| Alkaline phosphate – increase by factor | 1.1 – 2.0 x ULN | 2.1 – 3.0 x ULN | 3.1 – 10 x ULN | > 10 x ULN |
| Liver Function Tests –ALT, AST increase by factor | 1.1 – 2.5 x ULN | 2.6 – 5.0 x ULN | 5.1 – 10 x ULN | > 10 x ULN |
| Bilirubin – when accompanied by any increase in Liver Function Test increase by factor | 1.1 – 1.25 x ULN | 1.26 – 1.5 x ULN | 1.51 – 1.75 x ULN | > 1.75 x ULN |
| Bilirubin – when Liver Function Test is normal; increase by factor | 1.1 – 1.5 x ULN | 1.6 – 2.0 x ULN | 2.0 – 3.0 x ULN | > 3.0 x ULN |
| Cholesterol | 201 – 210 | 211 – 225 | > 226 | --- |
| Pancreatic enzymes – amylase, lipase | 1.1 – 1.5 x ULN | 1.6 – 2.0 x ULN | 2.1 – 5.0 x ULN | > 5.0 x ULN |

* The laboratory values provided in the tables serve as guidelines and are dependent upon institutional normal parameters. Institutional normal reference ranges should be provided to demonstrate that they are appropriate.

** The clinical signs or symptoms associated with laboratory abnormalities might result in characterisation of the laboratory abnormalities as Potentially Life Threatening (Grade 4). For example, a low sodium value that falls within a grade 3 parameter (125-129 mEq/L) should be recorded as a grade 4 hyponatremia event if the subject had a new seizure associated with the low sodium value.

ULN is the upper limit of the normal range.

| Haematology * | Mild (Grade 1) | Moderate (Grade 2) | Severe (Grade 3) | Potentially Life Threatening (Grade 4) |
|---|--------------------|-----------------------|---------------------|---|
| Haemoglobin (Female) - gm/dL | 11.0 – 12.0 | 9.5 – 10.9 | 8.0 – 9.4 | < 8.0 |

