| Haemoglobin (Female) change from baseline value - gm/dL | Any decrease – 1.5 | 1.6 – 2.0 | 2.1 – 5.0 | > 5.0 |
| Haemoglobin (Male) - gm/dL | 12.5 – 13.5 | 10.5 – 12.4 | 8.5 – 10.4 | < 8.5 |
| Haemoglobin (Male) change from baseline value – gm/dL | Any decrease – 1.5 | 1.6 – 2.0 | 2.1 – 5.0 | > 5.0 |
| WBC Increase - cell/mm ³ | 10,800 – 15,000 | 15,001 – 20,000 | 20,001 – 25,000 | > 25,000 |
| WBC Decrease - cell/mm ³ | 2,500 – 3,500 | 1,500 – 2,499 | 1,000 – 1,499 | < 1,000 |
| Lymphocytes Decrease - cell/mm ³ | 750 – 1,000 | 500 – 749 | 250 – 499 | < 250 |
| Neutrophils Decrease - cell/mm ³ | 1,500 – 2,000 | 1,000 – 1,499 | 500 – 999 | < 500 |
| Eosinophils - cell/mm ³ | 650 – 1500 | 1501 – 5000 | > 5000 | Hypereosinophilic |
| Platelets Decreased - cell/mm ³ | 125,000 – 140,000 | 100,000 – 124,000 | 25,000 – 99,000 | < 25,000 |
| PT – increase by factor (prothrombin time) | 1.0 – 1.10 x ULN | 1.11 – 1.20 x ULN | 1.21 – 1.25 x ULN | > 1.25 x ULN |
| PTT – increase by factor (partial thromboplastin time) | 1.0 – 1.2 x ULN | 1.21 – 1.4 x ULN | 1.41 – 1.5 x ULN | > 1.5 x ULN |
| Fibrinogen increase - mg/dL | 400 – 500 | 501 – 600 | > 600 | -- |
| Fibrinogen decrease - mg/dL | 150 – 200 | 125 – 149 | 100 – 124 | < 100 or associated with gross bleeding or disseminated intravascular coagulation (DIC) |

* The laboratory values provided in the tables serve as guidelines and are dependent upon institutional normal parameters. Institutional normal reference ranges should be provided to demonstrate that they are appropriate. ULN is the upper limit of the normal range.

iv. REFERENCES for the Appendix C

1. National Cancer Institute Common Toxicity Criteria, April 30, 1999. (<http://ctep.cancer.gov/reporting/CTC-3.html>).
2. Division of AIDS Table for Grading Severity of Adult Adverse Experiences; August 1992. (http://rcc.tech-res-intl.com/tox_tables.htm).
3. The Brighton Collaboration. Finalized Case Definitions and Guidelines. (http://brightoncollaboration.org/internet/en/index/definition_guidelines.html).
4. HIV Vaccine Trials Network Table for Grading Severity of Adverse Experiences; September 18, 2002. (http://rcc.tech-res-intl.com/tox_tables.htm).
5. Division of AIDS Table for Grading the Severity of Adult and Pediatric Adverse Events, December 2004. (http://www3.niaid.nih.gov/research/resources/DAIDSClinRsrch/PDF/Safety/DAIDS_AEGradingTable.pdf).

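### The laboratory limb of holding rule 2c names Grade 3 only, so read literally it leaves out subjects whose severe laboratory results are all Grade 4

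*Protocol*

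**What the plan says.** Rule 2c has two limbs joined by an or. The first counts Grade 3 unsolicited adverse events (AEs) that cannot reasonably be put down to something other than vaccination. The second counts "Any Grade 3 abnormality in pre-specified haematological or biochemical laboratory parameters* in an investigational group". The footnote lists haemoglobin, WBC, platelets, creatinine, ALT and AST. The threshold is 5 of 15 subjects in Step 1 and 8 of 30 in Step 2, with at least two subjects per group.

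Section 8.10.3 refers to Appendix C for laboratory grades. Table 26 there has four grades, and the fourth is labelled as potentially life threatening. The row for ALT and AST gives Grades 3 and 4 as "5.1 – 10 x ULN | > 10 x ULN", and the row for platelets gives "25,000 – 99,000 | < 25,000". Haemoglobin has two rows for each sex: one for the absolute value and one for the fall, for example "Haemoglobin (Female) change from baseline value - gm/dL".

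The iSRC checks the rules at each safety evaluation. It also reviews all available safety data unblinded and "will determine whether there is a safety signal that needs to be escalated". If it sees no signal, "the favourable outcome of the safety evaluation will be documented and provided in writing" (Section 8.10.2.1).

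**The concern.** The clinical intensity scales in Section 8.3.3.2.1 stop at Grade 3. In rules 2a, 2b and the AE limb of 2c, Grade 3 is therefore the top category and nothing lies above it. The laboratory limb uses the same words with a four-grade scale. Within any one row of Table 26 the bands do not overlap, so a Grade 4 value is not also Grade 3.

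A numeric holding rule should move toward its trigger as toxicity worsens. Here, a subject who goes from Grade 3 to Grade 4, with no other Grade 3 laboratory result, drops out of the laboratory count. The check is one of those made before Dose 2 and before Step 2, in a study that gives UspA2 to humans for the first time.

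**Working it through.** **1. The plan's own figures.** Section 8.10.4 gives the chance of not meeting rule 1. With n subjects and true incidence p this is (1 − p)^n.
- n = 15: 0.99^15 = 0.860 and 0.80^15 = 0.035. Stated: 86% and 3.5%.
- n = 30: 0.99^30 = 0.740 and 0.90^30 = 0.042. Stated: 74% and 4.2%.

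These agree, so the same binomial model is used below.

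**2. Bands for the six parameters (Table 26).**

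| Parameter | Grade 3 | Grade 4 |
|---|---|---|
| ALT, AST | 5.1–10 × ULN | > 10 × ULN |
| Creatinine, mg/dL | 2.1–2.5 | > 2.5 or dialysis |
| Platelets, /mm³ | 25,000–99,000 | < 25,000 |
| WBC increase, /mm³ | 20,001–25,000 | > 25,000 |
| WBC decrease, /mm³ | 1,000–1,499 | < 1,000 |
| Haemoglobin, female, g/dL | 8.0–9.4 | < 8.0 |
| Haemoglobin, male, g/dL | 8.5–10.4 | < 8.5 |
| Haemoglobin fall, g/dL | 2.1–5.0 | > 5.0 |

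**3. Who still counts in the laboratory limb.** A subject with Grade 4 ALT and Grade 3 AST counts through AST. Haemoglobin can be Grade 4 on one row and Grade 3 on the other. The examples assume that both rows are used; the footnote says only haemoglobin.
- Woman, 12.0 to 7.9: absolute Grade 4, fall 4.1 is Grade 3. Counts.
- Woman, 12.0 to 6.9: absolute Grade 4, fall 5.1 is Grade 4. Does not count.
- Man, 16.0 to 10.8: absolute Grade 2, fall 5.2 is Grade 4. Does not count.

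**4. Which sample applies.** The row limits the window to Day 0–Day 6, while Table 7 sets "Visit 1 (Day 0) → Visit 2 (Day 7) | 7 days | 7 - 9 days". The Figure 2 legend describes the safety evaluation as "including Day 7 post-vaccination laboratory assessments". The Day 7 sample is therefore taken as covered.

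**5. Effect on the count.** No rates are needed here.
- Step 1: 4 at Grade 3 plus 1 at Grade 4 only counts as 4. With Grade 4 included it is 5, and the threshold is met.
- Step 2: 7 plus 1 counts as 7. With Grade 4 included it is 8, and the threshold is met.

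**6. Illustration under assumed rates.** The documents give no laboratory toxicity rates. Let g3 and g4 be the shares of subjects whose worst laboratory grade is 3 and 4, and r the share of Grade 4 subjects who also have a Grade 3 laboratory result. As written, p = g3 + r·g4. With Grade 4 included, p = g3 + g4, the same as r = 1. The chance of reaching the threshold is P(X ≥ 5) for n = 15 and P(X ≥ 8) for n = 30, with X binomial. Results in percent:

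| g3 + g4 | 5/15, r = 0 | r = 0.5 | r = 1 | 8/30, r = 0 | r = 0.5 | r = 1 |
|---|---|---|---|---|---|---|
| 5% + 1% | 0.06 | 0.10 | 0.14 | 0.01 | 0.02 | 0.03 |
| 10% + 2% | 1.3 | 1.9 | 2.7 | 0.8 | 1.4 | 2.2 |
| 15% + 5% | 6.2 | 10.6 | 16.4 | 7.0 | 14.1 | 23.9 |
| 20% + 10% | 16.4 | 31.4 | 48.5 | 23.9 | 48.6 | 71.9 |

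These figures are for the laboratory limb alone. Subjects who would count through the AE limb are ignored.

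**The case against.** The strongest reply is that a Grade 4 subject has other ways to be counted or noticed.

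- **AE limb of rule 2c.** Under Section 8.1.4, a laboratory finding that the investigator judges clinically significant, without a diagnosis, is recorded as an AE if it meets the AE definition. If it is also rated severe and has no other reasonable cause, it counts toward the same 5/15 or 8/30. A platelet count below 25,000 could well be handled this way.
- **Rule 1a.** One life-threatening serious AE is enough. Section 8.1.2 requires actual risk of death at the time, so a number above a Grade 4 limit does not qualify by itself, but the worst cases may.
- **General review.** The iSRC sees all safety data unblinded and is not confined to the counts.

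All three stand. A reader might infer that a subject with only Grade 4 results is lost to rule 2c altogether, or that dosing would continue past Grade 4 toxicity. The documents do not support either reading, because of these routes. Each route, however, rests on someone's judgement of clinical significance, intensity, cause, seriousness or signal. The laboratory limb is the part of the rule that needs none of these, and they do not correct its count.

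A second reply is that the literal reading is selective: it takes Grade 3 strictly but Day 0–Day 6 loosely. The difference is that the Figure 2 legend gives textual support for including the Day 7 results, whereas no text supports counting Grade 4. The intent was nevertheless probably at least Grade 3, and that limits the weight of the point.

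**Conclusion.** The laboratory limb of rule 2c is wrong as written: applied exactly, it omits subjects whose severe laboratory results are all Grade 4. The severity is minor. The effect on the count is certain for such subjects, but its practical consequence is probably small.

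A reader might take the lower rows of the table as evidence that the rule loses much of its sensitivity. The documents do not support that. Those rows need 15% + 5% or 20% + 10% severe laboratory results, and subjects with clinically significant abnormalities are excluded at entry. At 5% + 1% the difference is at most 0.14 − 0.06 = 0.08 percentage points for 5/15, and it is zero if every Grade 4 subject also has a Grade 3 result.

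The conclusion rests on a literal reading of the grade and on the Day 7 sample being within the rule. The probabilities also rest on the assumed rates.

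**What to change.** In Table 22, change the laboratory limb of rule 2c to *any Grade 3 or higher (Grade 3 or Grade 4) abnormality*, and use the same definition in the iSRC counts. Leave 5/15 and 8/30 unchanged.

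The cost is a few words in the table and a matching line in the specification of the iSRC counts, which is not among the documents. No new data are needed. The downside is a marginally higher chance of a hold: for 5/15 at the lowest assumed rates, from 0.06% to 0.14% at most. If the intent was already Grade 3 or worse, the edit simply records it.
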